2.5. Antibiotic Resistance and the Resistome

The effect of antibiotic prophylaxis on bacterial resistance after OHCA are not known, but antibiotic resistance is a global concern.²⁵ Emergence of resistant bacteria will be examined in treatment and control patients. Control patients may be exposed to longer courses of broad spectrum antibiotics due to higher rates of pneumonia. Drug concentrations in stool, effects of ceftriaxone on expression of resistance genes, and on richness, diversity, and relative abundance of taxa will be quantified.

Prior studies have concluded antibiotic prophylaxis in acutely brain-injured patients does not induce bacterial resistance based on limited analyses. For example, in the trial examining cefuroxime prophylaxis, the intervention did not induce bacterial resistance based similar rates in gram-negative bacilli pneumonia in both groups.¹⁹ Advances in metagenomics allows for sample multiplexing and depth of sequence coverage (20 million reads) for the measurement of resistomes of each individual patient.

The ANTHARTIC trial evaluated intestinal acquisition of multidrug-resistant bacteria on day seven on solid selective media using stool samples, limiting their observations to conditionally cultivatable organisms.³ No difference was found following two days of amoxicillin-clavulanate administration compared to placebo. The contemporary gold standard for evaluating bacterial resistance is resistome analysis with high-throughput sequencing, which will be utilized in the PROTECT trial.

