2.7. Study Hypothesis and Anticipated Results

Prophylactic ceftriaxone administered within six hours of ICU admission will reduce the incidence of EOP and T cell-mediated inflammation in comatose OHCA survivors. Additionally, prophylactic ceftriaxone will not negatively affect bacterial resistomes as assessed by resistance genotypes in stool or sputum.

3. Trial Design

The PROTECT trial was a single-center, randomized-controlled, quadruple-blind, non-commercial superiority trial conducted at xxxx. The inflammation analysis will be completed at xxxx. The resistome analysis will be done at xxxx and xxxx.

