3.11.2. Secondary efficacy outcomes

- Days of antibiotic susceptibility coverage
- Microbiologically-confirmed EOP occurring <4 days after initiation of mechanical ventilation
- Microbiologically-confirmed late-onset pneumonia occurring ≥4 days after initiation of mechanical ventilation
- Clinically-diagnosed late-onset pneumonia occurring ≥4 days after initiation of mechanical ventilation
- Incidence of non-pulmonary infections
- ICU-free days in the first 28 days of admission
- Mechanical ventilator-free days in the first 28 days of admission
- ICU LOS
- Hospital LOS
- ICU mortality
- Hospital mortality
- Discharge disposition

- Home with services
- Home without services
- o Rehabilitation
- Skilled nursing care
- Hospice
- o Death
- o Transfer to another hospital
- Functional outcome at hospital discharge and six months post cardiac arrest (+/- 30 days)
 - Good functional outcome will be mRS ≤0-3 of or a CPC 1-2 (Appendices 16.1 and 16.2)
 - Functional outcome will be assessed by a research coordinator at hospital discharge and via telephone at six month follow up

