4.1. Specimen Handling and Transportation

Sputum sample and rectal swab will be collected prior to study drug initiation and 72-96 hours after administration of first dose of study drug (after study drug has been completed). A third rectal swab will be collected 144-168 hours after administering first dose of study drug or earlier in the case of death, comfort measures only or hospital discharge, after which no study procedures will be conducted. Missing time points do not disqualify patient for study participation and is not a protocol deviation. Total nucleic acids will be extracted and resistomes determined by shotgun metagenomic sequencing using super high-throughput methods. COVID-19 considerations are outlined in Appendix 16.7. Samples from non-XXXX hospitals may be stored and transported under various conditions not listed above but that are acceptable.

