4.2. Resistome Determination

Antibiotic resistance genes were measured in material recovered from rectal swabs collected prior to study drug initiation, after study drug completion (three days), and 6-7 days after the first dose of study drug. Total nucleic acids were extracted from rectal swabs using ZymoBIOMICS DNA/RNA plus extraction kit (Zymo Research Corporation 2024). Sequencing libraries were prepared using the Kapa BioSystems HyperPlus Kit (KR1145 -v3.16). Sequencing was completed on a NovaSeq 6000 with an SP flow cell (paired-end 250 bps reads). Data was demultiplexed using bcl2fastq v2.20.0.422. FASTQ files were examined for quality using FastQC v0.11.5 and multiqc v1.11 with default settings.^{49,50} Estimation of duplication rates, adapter sequence trimming and read merging was completed using fastp v0.23.2 with default settings and the flags '--include_unmerged', '--merge', '-I 50' and '-g' to remove poly-G tails produced by the NovaSeq platform.⁵¹ Human reads were identified by mapping the data against the human reference genome (GRCh38) using bwa mem v0.7.17 and filtering the mapped reads using samtools v1.19.2 (bit flags -f 4 -F262, -f 8 -F 260, and -f 12 and -F 256).^{52,53} Metagenomic assembly was completed from the unmapped reads using the SPAdes pipeline v3.15.5 with the metagenomic flag and default settings. QUAST v5.2.0 was utilized to characterize the contiguity of the genome assemblies.^{54,55} Per sequence coverage statistics were calculated using bwa mem v0.7.17 and samtools v1.19.2 with default settings. BLAST v2.14.0 was utilized to compare sequences against the nt database.⁵⁶ Blobtools v1.1.1 was then used to taxonomically classify each sequence using the 'bestsum' taxonomic rule and the NCBI taxonomy database.⁵⁷ Any human contigs were removed from the assemblies based on these taxonomic assignments. PROKKA v1.14.0 was used for CDS annotation. Antimicrobial resistance genes were characterized using AMRFinderPlus using both the genome assemblies (FASTA) and the annotated genes from PROKKA (FAA).^{58,59}

5. Inflammation Assessment

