8.1. Definitions

Adverse Event (per FDA 21CFR312.32)

Adverse event means any untoward medical occurrence associated with the use of a drug in humans, whether or not considered drug related.

Serious Adverse Event (per FDA 21CFR312.32)

An adverse event is considered "serious" if, in the view of either the investigator or sponsor (when applicable), it results in any of the following outcomes:

- Death (*see below exception)
- Life-threatening adverse event
- Inpatient hospitalization (*see below exceptions) or prolongation of existing hospitalization
- Persistent or significant incapacity or substantial disruption of the ability to conduct normal life functions (disability)
- Congenital anomaly/birth defect

Important medical events that may not result in death, be life-threatening, or require hospitalization may be considered serious when, based upon appropriate medical judgment, they may jeopardize the patient or subject and may require medical or surgical intervention to prevent one of the outcomes listed in this definition (above).

*Exception to the above serious adverse event definitions:

 An adverse event that results in death is usually considered a serious adverse event. However, 40-50% of patients who survive to the hospital after OHCA will not survive their hospital stay as a result of their underlying clinical condition. Since death is a clinical outcome for this study, deaths will not be reported as serious adverse events unless the investigator deems them related to study drug or study procedures.

Unexpected Adverse Event (per FDA 21CFR312.32)

An adverse event is considered "unexpected" if it is not listed in the investigator brochure or is not listed at the specificity or severity that has been observed; or, if an investigator brochure is not required or available, is not consistent with the risk information described in the general investigational plan or elsewhere in the current application, as amended.

Ceftriaxone is an FDA approved medication and does not have an investigator brochure. Therefore, the risk information is being provided in the protocol and informed consent form.

In addition, the unexpected adverse event definition assumes a causal relationship to the study drug (ceftriaxone). If an adverse event is not considered of Reasonable or Definite Relatedness to the ceftriaxone, it would not be considered an unexpected adverse event.

Relatedness

Relatedness	Description			

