9.5. Resistome Assessment

Abundance of antibiotic resistance-associated genotypes in resistomes will be compared within and between treatment groups. If ceftriaxone or placebo alters resistomes, ANOVA will be performed across genotypes. The abundance of each genotype will be compared between ceftriaxone- and placebo-treated patients post-intervention by both Student's T test and $\chi 2$ to establish direct changes associated with ceftriaxone and whether those deviate from potential changes in resistomes due to ICU admission. All statistical analyses will be performed using GraphPad Prism 8 (GraphPad Software Inc). A p value <0.05 will be considered significant. To measure the acquisition of ARGs, the increase in number of ARGs relative to baseline samples were compared within each treatment group using the Wilcoxon Signed-Ranks test. In addition, the baseline number and changes in the number of ARGs targeting a prioridefined frequently administered (macrolides, beta-lactams, fluoroquinolones, sulfamethoxazole-trimethoprim, and vancomycin) and infrequently administered (tetracyclines, erythromycin, aminoglycosides, chloramphenicol, clindamycin, fosfomycin, quinupristin) antibiotics according to clinical practice guidelines were compared between treatment groups.^{67,68}

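### The resistome tests in section 9.5 cannot show absence of harm, and their between-arm contrast measures a prophylaxis strategy rather than the direct effect of ceftriaxone

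*Combined protocol and SAP*

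**What the plan says.** Section 2.7 states the hypothesis that "prophylactic ceftriaxone will not negatively affect bacterial resistomes as assessed by resistance genotypes in stool or sputum". Section 9.5 compares the abundance of each genotype between arms after the intervention, by t test and chi-square at p<0.05, "to establish direct changes associated with ceftriaxone and whether those deviate from potential changes in resistomes due to ICU admission". It adds within-arm signed-rank tests on the number of resistance genes, and a between-arm comparison of genes grouped by antibiotic class. No interval, margin or rule for non-study antibiotics is given there. Section 9.2 specifies 95% intervals for the early-onset pneumonia (EOP) risk ratio, and section 9.3 carries that approach over to the other infectious outcomes, but not to the resistome.

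On antibiotics outside the study drug, section 2.5 says: "Control patients may be exposed to longer courses of broad spectrum antibiotics due to higher rates of pneumonia". Section 8.3 stops study drug when an infection calls for a different regimen and keeps collecting sputum and rectal samples. Section 4.2 places the post-baseline swabs "after study drug completion (three days), and 6-7 days after the first dose of study drug". The secondary outcome "Days of antibiotic susceptibility coverage" (3.11.2, with a matching item in 6.4) records antibiotic exposure, but 9.5 does not use it.

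**The concern.** There are two separate problems.

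**Absence of harm.** The hypothesis asserts no harm, but the tests can only detect a difference. A p value of 0.05 or more is what a harmless drug would usually give. It is also what a moderately harmful drug would often give at this sample size. Without an interval the reader cannot tell the two apart.

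**Attribution.** Reading the between-arm difference as ceftriaxone's direct effect, with placebo standing for ICU admission, requires that placebo patients differ from the others only in not receiving ceftriaxone. The plan expects otherwise. If prophylaxis works, more control patients develop pneumonia and may receive treatment antibiotics, and those antibiotics can change the resistome too. The within-arm tests do not solve this, because the same treatment antibiotics act within each arm.

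Section 2.2 presents the risk to the resistome as the counterweight to the benefit of prophylaxis, and section 11 puts the resistome data in the main publication. What the trial may conclude about that risk therefore matters.

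**Working it through.** **Inputs.** 60 per arm, and EOP of 55% v 30% with 80% power at two-sided 5% (section 9.1). The cited prior trial's five-day EOP was 31% v 17% (section 9.1). The documents give no resistome SD, effect size, margin or treatment rate, so resistome figures are in SD units or for an assumed 50% prevalence.

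**The plan's own figure.** n per arm = [1.96√(2 × 0.425 × 0.575) + 0.842√(0.55 × 0.45 + 0.30 × 0.70)]² / 0.25² = 61 after rounding up. Power at 60 is 79.9%. The sample size reproduces, but it was set for EOP and not for the resistome.

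**Precision of a resistome difference.** For the t test the 95% half-width is t(0.975, 2n−2) × √(2/n). For the chi-square comparison at 50% prevalence it is 1.96 × √(2 × 0.25/n).

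| Swabs per arm | Half-width, SD | Half-width, percentage points |
|---|---|---|
| 60 | 0.36 | 18 |
| 45 | 0.42 | 21 |
| 30 | 0.52 | 25 |

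The rows for 45 and 30 are scenarios with 25% and 50% of swabs missing, not predictions.

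**How often real harm would be missed.** With 60 per arm, √(2/60) = 0.183. A true shift of 0.3 SD gives power of about Φ(0.3/0.183 − 1.96) = 38%, so about 62% of such trials would give p≥0.05. For true shifts of 0.2 and 0.5 SD the figures are 81% and 22%.

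**What a margin would need.** For one-sided 0.025, 80% power and no true difference, n per arm = 2(1.96 + 0.842)²/m². This gives 393, 175 and 63 for margins of 0.2, 0.3 and 0.5 SD. Only the loosest of these is near 60.

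**Attribution: the sections side by side.** The schedule in section 13 marks EOP at 0-24, 24-48 and 48-72 h after the first dose. The first post-baseline samples are at 72-96 h and the third swab at 144-168 h (4.1). Treatment of EOP can therefore precede both, with less time to act before the first. Sections 2.5 and 8.3 show that such treatment is expected and that sampling continues through it.

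**Illustration only.** Let ceftriaxone shift a genotype by d, let a treatment course shift it by t in either arm, and let a share s of EOP patients be treated early enough to affect the swab. The difference is (d + 0.30st) − 0.55st = d − 0.25st at the design rates, or d − 0.14st at the cited rates. If t has the same sign as d, the contrast shrinks. If d = 0 and t > 0, the contrast favours ceftriaxone. Assume t = d, EOP spread evenly over 0-72 h, and 48 h of treatment needed to matter. Then s = (72−48)/72 = 0.33 to (96−48)/72 = 0.67 at the 72-96 h sample. The shrinkage is 0.25s = 8-17%, or 0.14s = 5-9%. Every one of these assumptions is unverified.

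**The case against.** The strongest reply is that nothing is wrong with the comparison itself. Randomisation makes the between-arm contrast valid as the effect of assignment. The wording in 9.5 is partly hedged, since it speaks of association and of potential changes. In context, direct could mean between arms as opposed to before-and-after, and ICU admission could mean usual ICU care, including treatment of infection. Section 1 already describes the comparator as standard care, and section 2.5 shows that the authors had control-arm antibiotics in mind. Nor does 9.5 say that p≥0.05 will be read as no harm.

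Most of this stands and limits the point. The first part concerns what may be concluded, and the second concerns interpretation. But the softer reading of 9.5 is not the natural one, and awareness in 2.5 is not carried into 9.5. Once 2.7 hypothesises no harm and 9.5 offers only difference tests, the plan has no means of supporting its hypothesis.

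Three stronger readings should be resisted.

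- **That the contrast is badly diluted towards no effect.** Larger figures, such as 25% at t = d, require every EOP case to be treated before the swab. At the 72-96 h sample even the illustration gives less. EOP is defined as under 4 days from ventilation (3.11.1). Spread over 0-96 h instead, s is 0.25-0.5 and the shrinkage at the design rates is 6-12.5%. The 55% v 30% figures are diagnosis rates, not treatment rates.
- **That half the swabs will be missing because** "40-50% of patients who survive to the hospital after OHCA will not survive their hospital stay". Death in hospital does not imply a missing swab. Patients unlikely to survive 48 h are excluded (3.2), support generally continues for at least 72 h (3.14), and the third swab is taken "or earlier in the case of death, comfort measures only or hospital discharge".
- **That the intention-to-treat comparison is invalid.** It is not. Only the label on it is.

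**Conclusion.** The point holds as a correction to reporting and interpretation. Section 9.5 cannot support the no-harm hypothesis in 2.7. At best the half-width is about 0.36 SD, or 18 points at 50% prevalence, and a true harmful shift of 0.3 SD would be non-significant in about 62% of trials. This rests on 60 swabs per arm and two-sided 5% tests, and it holds even if no patient receives open-label antibiotics.

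Separately, the between-arm contrast is prophylaxis versus antibiotics on diagnosis, and should not be read as direct ceftriaxone effect against ICU admission. That follows from the text of 2.5, 4.1, 8.3 and 13 and needs no numerical assumption. The size and direction of any distortion cannot be determined from the documents, and the dilution percentages are not evidence of either. The primary outcome, safety monitoring and trial conduct are unaffected. The change is worth making because it is cheap and alters what may be concluded about resistance.

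**What to change.** 1. In 9.5, report between-arm differences with 95% confidence intervals at each post-baseline time point, and state that p≥0.05 will not be taken as showing absence of harm. Estimation is more realistic than a margin, because the tighter margins above need far more than 60 per arm.
2. Describe the all-patient contrast as a treatment-policy effect (prophylaxis versus antibiotics on diagnosis), and remove the language of direct change and of change caused by ICU admission.
3. Tabulate open-label antibiotic exposure (agent and days) by arm up to each swab, from the records already used for antibiotic coverage days. Any analysis limited to swabs taken before the first open-label antibiotic should be optional and labelled exploratory, since it selects on a post-randomisation event.

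The cost is SAP wording, intervals for comparisons already planned, and some extra abstraction of start and stop dates. No new patients, samples or assays are needed. The downside is a more cautious conclusion: the trial may be unable to say that ceftriaxone has no negative effect on the resistome.

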3.8.2. Rationale for selection

Ceftriaxone was selected for many reasons: 1) bactericidal activity against commonly isolated bacteria in comatose OHCA patients, 2) generic availability and low cost, 3) ease of administration over 30 minutes, 4) favorable local susceptibility profile, 5) excellent safety data, and 6) potentially neuro-protective.³⁷

Although informative, data from the TTM trial included isolates through 14 days of admission and ANTHARTIC through 7 days of admission.³ Prophylactic antibiotics are intended to prevent EOP due to less resistant, community-acquired bacteria. Bacteria isolated after 72-96 hours of ICU admission tend to be more resistant and healthcare-associated.³⁸

Bacteria	TTM Trial ¹	ANTHARTIC Trial ¹	xxxx Ceftriaxone Susceptibility ²
Gram-positive			
Staphylococcus aureus	22.9%	12%	86%
Streptococcus pneumoniae	5.5%	7%	99%
Streptococcus agalactiae	1.5%	3%	not reported
Gram-negative			
Haemophilus influenzae	9.1%	22%	100%
Escherichia coli	9.1%	11%	93%
Klebsiella pneumoniae	5.1%	4%	94%
Serratia marcescens	5.1%	3%	89%
Klebsiella oxytoca	3.6%	1%	97%
Enterobacter cloacae	3.3%	3%	78%
Pseudomonas aeruginosa	2.5%	3%	not active
Enterobacter aerogenes	2.2%	2%	75%
Proteus mirabilis	2.2%	1%	98%
Moraxella catarrhalis	1.5%	1%	not reported

¹ Percentages do not equal 100 for each study as some organisms (e.g., fungi) were not included above

² xxxx ceftriaxone antibiogram data through December 2019

TTM = targeted temperature management

The ceftriaxone dose of 2 gm IV q12h was selected using internal antibiogram data at XXXX, as well as the cumulative fraction of response based on dose. These data appear below:

Regimen	Cumulative Fraction of Response
Ceftriaxone 1 gm IV q24h	8%
Ceftriaxone 2 gm IV q24h	45%
Ceftriaxone 2 gm IV q12h	86%

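### Section 9.5 measures acquisition of resistance genes by a net count, so newly gained genes can be cancelled by lost ones and acquisition can read as zero or negative

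*Combined protocol and SAP*

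**What the plan says.** Section 9.5 introduces its measure with "To measure the acquisition of ARGs, the increase in number of ARGs relative to baseline samples" and says these increases "were compared within each treatment group using the Wilcoxon Signed-Ranks test". The next sentence begins "In addition, the baseline number and changes in the number of ARGs targeting a" and goes on to two pre-set groups of antibiotics, those given frequently and infrequently, compared between arms. Earlier in the same section, "The abundance of each genotype will be compared between ceftriaxone- and placebo-treated patients post-intervention", by t test and chi-square.

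Section 4.2 gives the source data: "rectal swabs collected prior to study drug initiation, after study drug completion (three days), and 6-7 days after the first dose of study drug". It adds that "Antimicrobial resistance genes were characterized using AMRFinderPlus", so the plan identifies individual genes and not only a total.

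The hypothesis in section 2.7 is that "prophylactic ceftriaxone will not negatively affect bacterial resistomes". No section defines acquisition as genes present after treatment and absent before it, and none counts gained and lost genes separately.

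**The concern.** Acquisition means that a patient now carries a resistance gene that was not there before. The quantity in section 9.5 is the number after minus the number before, so each lost gene cancels one gained gene. A patient who gains 8 genes and loses 12 scores -4, which reads as no acquisition.

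An antibiotic could plausibly cause both changes, removing susceptible organisms with the genes they carry while letting resistant organisms expand. Section 3.8.2 lists "bactericidal activity against commonly isolated bacteria in comatose OHCA patients" among the reasons for choosing ceftriaxone. If losses were heavier in that arm, the cancellation would favour the hypothesis of no negative effect. At stake is whether a flat or falling ARG count could be reported as evidence that no resistance was acquired.

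**Working it through.** **Which reading fits the text.** The wording could be stretched to mean the number of new genes. But that number is never negative, so a signed-rank test against baseline would be close to meaningless. The following sentence speaks of changes in number. Both point to a net count.

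**Identity.** Net change = gained - lost. This needs no assumption: 5 gained and 5 lost gives 0; 5 gained and 8 lost gives -3.

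**No plan figure to reproduce.** The only power figure, in section 9.1, concerns early-onset pneumonia. The documents give no ARG counts, so every rate below is an assumption.

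**Illustration.** Inputs: 40 paired patients per arm; mean 40 baseline ARGs; true gains of 8 on ceftriaxone and 3 on placebo; placebo loses 10%; perfect detection; Poisson baselines, binomial losses, overdispersed Poisson gains; 800 trials per setting. Expected net change is 8 - 40 x loss on ceftriaxone and 3 - 40 x 0.10 = -1 on placebo.

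| Ceftriaxone loss | Net change, ceftriaxone | Between-arm net difference (true gain difference 5) | Planned within-arm test |
|---|---|---|---|
| 10% | 8 - 4 = +4 | +4 - (-1) = +5 | increase in 97% of trials |
| 20% | 8 - 8 = 0 | 0 - (-1) = +1 | increase in 0.4% |
| 30% | 8 - 12 = -4 | -4 - (-1) = -3 | increase never; decrease in 94% |

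With a different assumed spread of gains, the within-arm results are an increase in over 99% at 10% loss, 55% at 15% (net +2) and under 2% at 20%, and a decrease in 98% at 30%. In that run a between-arm test of net change at 30% loss favours ceftriaxone in 85% of trials, so moving to a between-arm test does not cure the fault. A between-arm test of gained genes detects 8 v 3 in over 99%.

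**Second set of assumptions.** With a baseline of 20, a gain of 4 and 60 patients, net change is +3, +2, 0 and -2 at 5%, 10%, 20% and 30% loss. At 20% loss, 56% of patients who gained a gene score zero or below. At 5-10% loss the increase is still found in all runs, but understated.

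**Does counting gained genes have its own bias?** Let d be the chance that a gene present is detected, B the number of true baseline genes and q the fraction lost. A gene missed at baseline counts as gained only if it persists and is then detected, so expected false gains are B(1 - d)(1 - q)d. Take B = 40, d = 0.8 and equal true gains of 3:
- False gains: 40 x 0.2 x 0.7 x 0.8 = 4.48 at 30% loss (ceftriaxone) and 40 x 0.2 x 0.9 x 0.8 = 5.76 at 10% loss (placebo), a spurious difference of -1.28.
- Net count, d(gain - Bq): 0.8 x (3 - 12) = -7.2 and 0.8 x (3 - 4) = -0.8, a difference of -6.4.

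The distortion of the gained count is thus (1 - d) = one fifth of that of the net count. It still matters: the gained-gene test wrongly shows fewer gains on ceftriaxone in about 48% of trials, against 100% for the net count. With true gains of 8 v 3 and 80% detection, the gained-gene test finds the difference in 82-96% of trials at 20-30% loss. With 50 baseline genes and 30% loss, one simulation put it at about 45%.

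**The case against.** Four points can be made for the plan.

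**Other analyses cover part of the gap.** The abundance comparison is made gene by gene between randomised arms, so enrichment of one gene is not cancelled by loss of another. Section 9.5 also opens with abundance compared within as well as between groups, and section 2.5 promises richness and diversity of taxa, which could reveal a loss of organisms. This stands. A reader might infer that the plan hides new resistance genes altogether; the documents do not support that. What remains is that no analysis counts new genes per patient, and the drug-class comparison still nets gains against losses within each group.

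**Net change is a legitimate measure of burden.** The hypothesis concerns negative effects on the resistome, not acquisition alone. This also stands. The fault is to call the net count acquisition and to report no measure of acquisition beside it.

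**The direction is not shown.** A reader might infer that cancellation is greater under ceftriaxone and that the measure therefore leans toward the hypothesis. That is plausible for a bactericidal drug, but no section says that ceftriaxone removes ARGs from rectal samples. Section 2.5 points partly the other way: controls may receive longer broad-spectrum courses because of more pneumonia, and could lose genes too.

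**The resistome is not a listed outcome in section 3.11.** True, but it is in the title and in the hypothesis, and section 11 places it in the main publication.

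**Conclusion.** The point holds as a fault of definition. The stated quantity is gained minus lost, and it cannot support a statement about acquisition in either direction. That conclusion rests on the wording and arithmetic alone.

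The size is conditional. Under the assumed counts the net measure works at 10% loss, shows almost no increase at 20% and a significant decrease at 30%, while true gains stay the same. The documents do not say which case applies or which arm loses more, so a bias toward the hypothesis is a possibility and not a finding. Nor should the gained-gene count be taken as unbiased: its detection rate of over 99% assumes perfect detection. The change should be made because it alters what can be concluded about resistance, but it does not touch the primary outcome.

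**What to change.** In section 9.5:
- Define acquisition, per patient, as the number of distinct ARGs detected in a post-drug swab and absent from that patient's baseline swab. Define loss as the reverse.
- Compare gained genes between arms at each post-drug time point (after drug completion and at 6-7 days) with an estimate and 95% CI, overall and for beta-lactam ARGs, the class of the study drug.
- Report losses beside gains, by arm and time point.
- Keep net change in number as a descriptive summary, and do not call it acquisition.
- State that a gene missed at baseline counts as gained only if it persists. Under imperfect detection the arm with more loss then has fewer false gains, and the comparison is biased in that arm's favour, though less than the net count is. Gained and lost counts are therefore to be read together.

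The cost is a few sentences and a short script on gene lists that section 4.2 already produces. No new samples or sequencing are needed.
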